**12.0 DATA AND SAFETY MONITORING**

In compliance with the Washington University Institutional Data and Safety Monitoring Plan, the Principal Investigator will provide a Data and Safety Monitoring (DSM) report to the Washington University Quality Assurance and Safety Monitoring Committee (QASMC) semi-annually beginning six months after accrual has opened (if at least one patient has been enrolled) or one year after accrual has opened (if no patients have been enrolled at the six-month mark).

The Principal Investigator will review all patient data at least every six months, and provide a semi-annual report to the QASMC. This report will include:

- HRPO protocol number, protocol title, Principal Investigator name, data coordinator name, regulatory coordinator name, and statistician
- Date of initial HRPO approval, date of most recent consent HRPO approval/revision, date of HRPO expiration, date of most recent QA audit, study status, and phase of study
- History of study including summary of substantive amendments; summary of accrual suspensions including start/stop dates and reason; and summary of protocol exceptions, error, or breach of confidentiality including start/stop dates and reason
- Study-wide target accrual and study-wide actual accrual
- Protocol activation date
- Average rate of accrual observed in year 1, year 2, and subsequent years
- Expected accrual end date
- Objectives of protocol with supporting data and list the number of participants who have met each objective
- Measures of efficacy
- Early stopping rules with supporting data and list the number of participants who have met the early stopping rules
- Summary of toxicities
- Abstract submissions/publications
- Summary of any recent literature that may affect the safety or ethics of the study

The study principal investigator and Research Patient Coordinator will monitor for serious toxicities on an ongoing basis. Once the principal investigator or Research Patient Coordinator becomes aware of an adverse event, the AE will be reported to the HRPO and QASMC according to institutional guidelines.

### **13.0 REGULATORY AND REPORTING REQUIREMENTS**

The entities providing oversight of safety and compliance with the protocol require reporting as outlined below. Please refer to Appendix C for definitions and Appendix D for a grid of reporting timelines.

Adverse events will be tracked from start of treatment through 28 days following discontinuation of study drug flotetuzumab. All adverse events—including adverse events associated with administration of DLI—must be recorded on the toxicity tracking case report form (CRF) with the exception of baseline adverse events, including any events related to allogeneic hematopoietic cell transplantation (allo-HCT), which shall be recorded on the medical history CRF.

Refer to the data submission schedule in Section 9 for instructions on the collection of AEs in the EDC.

### **13.1 Reporting to the Human Research Protection Office (HRPO) at Washington University**

Reporting will be conducted in accordance with Washington University IRB Policies.

Pre-approval of all protocol exceptions must be obtained prior to implementing the change.

### **13.2 Reporting to the Quality Assurance and Safety Monitoring Committee (QASMC) at Washington University**

The Sponsor Investigator (or designee) is required to notify the QASMC of any unanticipated problems involving risks to participants or others occurring at WU or any BJH or SLCH institution that has been reported to and acknowledged by HRPO. (Unanticipated problems reported to HRPO and withdrawn during the review process need not be reported to QASMC.)

QASMC must be notified within **10 days** of receipt of IRB acknowledgment via email to [[contact]](mailto:[contact]). Submission to QASMC must include the myIRB form and any supporting documentation sent with the form.

### **13.3 Reporting to MacroGenics, Inc.**

Immediately reportable events (IREs) are events that must be reported immediately to MacroGenics Product Safety or designee within 24 hours of being identified. IREs include:

- SAEs
- Pregnancy in a study patient or partner (Note: If the female partner of a male patient becomes pregnant, the partner must be requested to complete a Pregnant Partner Consent Form so that pregnant partner, fetal and/or newborn information can be collected.) Upon confirmation of serum pregnancy testing, the patient will be followed for the outcome of pregnancy. All live newborns will be followed six months after the birth, and all necessary information will be collected to assess the effects of study drug on the newborn. If necessary, the follow-up period will be extended for the newborn.

See Appendix C for definitions of AE, SAE, SUSAR.

Contact information for MacroGenics Product Safety is below:

- **Email:** [contact] (**preferred transmission**) or
- **[contact]

### **13.4 Reporting to the FDA**

The conduct of the study will comply with all FDA safety reporting requirements. **PLEASE NOTE THAT REPORTING REQUIREMENTS FOR THE FDA DIFFER FROM REPORTING REQUIREMENTS FOR HRPO/QASMC.** It is the

responsibility of the Washington University Sponsor-Investigator to report to the FDA as follows:

- Report any unexpected fatal or life-threatening suspected adverse reaction (refer to Appendix C for definitions) no later than **7 calendar days** after initial receipt of the information.
- Report a suspected adverse reaction that is both serious and unexpected (SUSAR, refer to Appendix C) no later than **15 calendar days** after it is determined that the information qualifies for reporting. Report an adverse event (refer to Appendix C) as a suspected adverse reaction only if there is evidence to suggest a causal relationship between the drug and the adverse event, such as:
  - A single occurrence of an event that is uncommon and known to be strongly associated with drug exposure
  - One or more occurrences of an event that is not commonly associated with drug exposure but is otherwise uncommon in the population exposed to the drug
  - An aggregate analysis of specific events observed in a clinical trial that indicates those events occur more frequently in the drug treatment group than in a concurrent or historical control group
- Report any findings from epidemiological studies, pooled analysis of multiple studies, or clinical studies that suggest a significant risk in humans exposed to the drug no later than **15 calendar days** after it is determined that the information qualifies for reporting.
- Report any findings from animal or in vitro testing that suggest significant risk in humans exposed to the drug no later than **15 calendar days** after it is determined that the information qualifies for reporting.
- Report any clinically important increase in the rate of a serious suspected adverse reaction of that listed in the protocol or IB within **15 calendar days** after it is determined that the information qualifies for reporting.

Submit each report as an IND safety report in a narrative format or on FDA Form 3500A or in an electronic format that FDA can process, review, and archive. Study teams must notify the Siteman Cancer Center Protocol Development team of each potentially reportable event within 1 business day after initial receipt of the information, and must bring the signed 1571 and FDA Form 3500A to the Siteman Cancer Center Protocol Development team no later than 1 business day prior to the due date for reporting to the FDA.

Each notification to FDA must bear prominent identification of its contents (“IND Safety Report”) and must be transmitted to the review division in the Center for Drug Evaluation and Research (CDER) or in the Center for Biologics Evaluation and Research (CBER) that has responsibility for review of the IND. Relevant follow-up information to an IND safety report must be submitted as soon as the information is available and must be identified as such (“Follow-up IND Safety Report”).

### **Acknowledgements**

We would like to thank the Alvin J. Siteman Cancer Center at Washington University School of Medicine and Barnes-Jewish Hospital in St. Louis, Missouri, for the use of the Clinical Trials Core, which provided protocol development services. The Siteman Cancer Center is supported in part by an NCI Cancer Center Support Grant #P30 CA91842.

## APPENDIX A: ECOG Performance Status Scale

Grade	Description
0	Normal activity. Fully active, able to carry on all pre-disease performance without restriction.
1	Symptoms, but ambulatory. Restricted in physically strenuous activity, but ambulatory and able to carry out work of a light or sedentary nature (e.g., light housework, office work).
2	In bed <50% of the time. Ambulatory and capable of all self-care, but unable to carry out any work activities. Up and about more than 50% of waking hours.
3	In bed >50% of the time. Capable of only limited self-care, confined to bed or chair more than 50% of waking hours.

4	100% bedridden. Completely disabled. Cannot carry on any self-care. Totally confined to bed or chair.
5	Dead.

## APPENDIX B: Revised International Prognostic Scoring System (IPSS-R)

IPSS-R Prognostic Score Values							
Prognostic Variable	Score						
	0	0.5	1.0	1.5	2.0	3.0	4.0
Cytogenetics*	Very good		Good		Intermediate	Poor	Very poor
Bone marrow blast (percent)	≤2		>2 to <5		5 to 10	>10	
Hemoglobin (g/dL)	≥10		8 to <10	<8			
Platelets (cells/microL)	≥100	50 to <100	<50				
ANC (cells/microL)	≥0.8	<0.8					

\*See cytogenetics in table below (MDS Cytogenetic Scoring System) for classifications.

MDS Cytogenetic Scoring System	
Prognostic subgroups	Cytogenetic Abnormalities
Very good	–Y, del(11q)
Good	Normal, del(5q), del(12p), del(20q), double including del(5q)
Intermediate	del(7q), +8, +19, i(17q), any other single or double independent clones
Poor	–7, inv(3)/t(3q)/del(3q), double including –7/del(7q), complex: 3 abnormalities
Very poor	Complex: > 3 abnormalities

IPSS-R Prognostic Risk Categories/Scores	
Risk Category	Risk Score
Very low	≤ 1.5
Low	>1.5 – 3
Intermediate	> 3 – 4.5
High	> 4.5 – 6
Very high	> 6

Taken from: Greenberg PL, Tuechler H, Schanz J, Sanz G, Garcia-Manero G, Sole F, et al. Revised international prognostic scoring system for myelodysplastic syndromes. *Blood*. 2012;120(12):2454-65.

## APPENDIX C: Definitions for Adverse Event Reporting

### A. Adverse Events (AEs)

As defined in 21 CFR 312.32:

**Definition:** any untoward medical occurrence associated with the use of a drug in humans, whether or not considered drug-related.

**Grading:** the descriptions and grading scales found in the revised NCI Common Terminology Criteria for Adverse Events (CTCAE) version 5.0 will be utilized for all toxicity reporting. A copy of the CTCAE version 5.0 can be downloaded from the CTEP website.

**Attribution (relatedness), Expectedness, and Seriousness:** the definitions for the terms listed that should be used are those provided by the Department of Health and Human Services' Office for Human Research Protections (OHRP). A copy of this guidance can be found on OHRP's website:

<http://www.hhs.gov/ohrp/policy/advevntguid.html>

### B. Suspected Adverse Reaction (SAR)

As defined in 21 CFR 312.32:

**Definition:** any adverse event for which there is a reasonable possibility that the drug caused the adverse event. "Reasonable possibility" means there is evidence to suggest a causal relationship between the drug and the adverse event. "Suspected adverse reaction" implies a lesser degree of certainty about causality than adverse reaction, which means any adverse event caused by a drug.

### C. Life-Threatening Adverse Event / Life Threatening Suspected Adverse Reaction

As defined in 21 CFR 312.32:

**Definition:** any adverse drug event or suspected adverse reaction is considered "life-threatening" if, in the view of the investigator, its occurrence places the patient at immediate risk of death. It does not include an adverse event or suspected adverse reaction that, had it occurred in a more severe form, might have caused death.

### D. Serious Adverse Event (SAE) or Serious Suspected Adverse Reaction

As defined in 21 CFR 312.32:

**Definition:** an adverse event or suspected adverse reaction is considered "serious" if, in the view of the investigator, it results in any of the following outcomes:

- Death
- A life-threatening adverse event

- Inpatient hospitalization or prolongation of existing hospitalization
- A persistent or significant incapacity or substantial disruption of the ability to conduct normal life functions
- A congenital anomaly/birth defect
- Any other important medical event that does not fit the criteria above but, based upon appropriate medical judgment, may jeopardize the subject and may require medical or surgical intervention to prevent one of the outcomes listed above

#### **E. Protocol Exceptions**

**Definition:** A planned change in the conduct of the research for one participant.

#### **F. Deviation**

**Definition:** Any alteration or modification to the IRB-approved research without prospective IRB approval. The term “research” encompasses all IRB-approved materials and documents including the detailed protocol, IRB application, consent form, recruitment materials, questionnaires/data collection forms, and any other information relating to the research study.

A minor or administrative deviation is one that does not have the potential to negatively impact the rights, safety, or welfare of participants or others or the scientific validity of the study.

A major deviation is one that does have the potential to negatively impact the rights, safety, or welfare of participants or others or the scientific validity of the study

## APPENDIX D: Reporting Timelines

Expedited Reporting Timelines				
Event	HRPO	QASMC	FDA	MacroGenics, Inc.
Serious AND unexpected suspected adverse reaction			Report no later than 15 calendar days after it is determined that the information qualifies for reporting	Report within 24 hours of being identified to [contact]
Unexpected fatal or life-threatening suspected adverse reaction			Report no later than 7 calendar days after initial receipt of the information	Report within 24 hours of being identified to [contact]
Unanticipated problem involving risk to participants or others	Report within 10 working days. If the event results in the death of a participant enrolled at WU/BJH/SLCH, report within 1 working day.	Report via email after IRB acknowledgment		
Pregnancy				Report within 24 hours of being identified to [contact]
Major deviation	Report within 10 working days. If the event results in the death of a participant enrolled at WU/BJH/SLCH, report within 1 working day.			
A series of minor deviations that are being reported as a continuing noncompliance	Report within 10 working days.			
Protocol exception	Approval must be obtained prior to implementing the change			

Expedited Reporting Timelines				
Event	HRPO	QASMC	FDA	MacroGenics, Inc.
Clinically important increase in the rate of a serious suspected adverse reaction of that list in the protocol or IB			Report no later than 15 calendar days after it is determined that the information qualifies for reporting	
Complaints	If the complaint reveals an unanticipated problem involving risks to participants or others OR noncompliance, report within 10 working days. If the event results in the death of a participant enrolled at WU/BJH/SLCH, report within 1 working day. Otherwise, report at the time of continuing review.			
Breach of confidentiality	Within 10 working days.			
Incarceration	If withdrawing the participant poses a safety issue, report within 10 working days.  If withdrawing the participant does not represent a safety issue and the patient will be withdrawn, report at continuing review.			

Routine Reporting Timelines			
Event	HRPO	QASMC	FDA
Adverse event or SAE that does not require expedited reporting	If they do not meet the definition of an unanticipated problem involving risks to participants or others, report summary information at the time of continuing review	Adverse events will be reported in the toxicity table in the DSM report which is typically due every 6 months.	The most current toxicity table from the DSM report is provided to the FDA with the IND's annual report.
Minor deviation	Report summary information at the time of continuing review.		
Complaints	If the complaint reveals an unanticipated problem involving risks to participants or others OR noncompliance, report within 10 working days. If the event results in the death of a participant enrolled at WU/BJH/SLCH, report within 1 working day. Otherwise, report at the time of continuing review.		
Incarceration	If withdrawing the participant poses a safety issue, report within 10 working days.  If withdrawing the participant does not represent a safety issue and the patient will be withdrawn, report at continuing review.		

## APPENDIX E: Neurotoxicity Grading and Management

Grade 1	Grade 2	Grade 3	Grade 4
Decreased LOC, awakens spontaneously ICE score 7-9 (see table below for ICE scoring parameters)	Decreased LOC, awakens to voice ICE score 3-6	Decreased LOC, awakens only to tactile stimulus ICE score 0-2 Seizure: transient Cerebral Edema on imaging	Decreased LOC, unarousable ICE score 0 Seizure: prolonged (>5 minutes) or recurrent Cerebral Edema on imaging Focal neurologic weakness/deficits
Slow infusion by 10-20%  Frequent neuro checks  Supportive care  Consider seizure prophylaxis (e.g. Levetiracetam 1000mg twice daily)	Slow infusion by 25-50%  Obtain brain MRI, LP (with opening pressure) and EEG  Neuro checks, including fundoscopy and Glasgow coma scale assessments  Start telemetry and continuous SpO2 monitoring  If concurrent CRS, administer Tocilizumab and Consider steroids per CRS algorithm  Administer seizure prophylaxis, or increase dose if already started	Stop infusion  Manage as Grade 2, plus:  If concurrent CRS, administer Tocilizumab and administer steroids per CRS algorithm  Consider ICU care	Manage as Grade 3, plus:  Consider high dose steroids plus CRS algorithm management (e.g. Methylprednisolone 1000mg IV daily x3 days, then rapid taper over 6 days)  Treat cerebral edema  Transfer to ICU care with aggressive supportive care

LOC: level of consciousness; MRI: magnetic resonance imaging; LP: lumbar puncture; EEG: electroencephalogram

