## 2.0 OBJECTIVES AND ENDPOINTS

Objectives	Endpoints
Primary	
To evaluate the efficacy of flotetuzumab in post-allo-HCT relapsed AML and MDS following Cycle 1 of flotetuzumab (Cycle 1 Day 28 assessment).	Efficacy assessed via composite endpoint of CR and CRi (Cycle 1 Day 28 assessment)
Secondary	

 
• To evaluate the efficacy of flotetuzumab monotherapy in post-allo-HCT relapsed AML and MDS following Cycle 2.
 
• To evaluate the safety and tolerability of flotetuzumab +/- DLI in the post-allo-HCT setting.
 
	
 
• Efficacy assessed at Cycle 2 Day 28 (or at C1 D28 in patients who receive only one cycle):               
 
○ Composite endpoint of CR and CRi at C2 D28
 
○ Overall Response (OR) Rate (defined as PR or greater)
 
○ Morphologic leukemia-free state (MLFS) Rate
 
○ Partial Response (PR) Rate
 
○ Stable Disease (SD) Rate
 
○ Progression Free Survival (PFS)
 
○ Overall Survival (OS)
 
 
 
• Safety and tolerability as assessed by:               
 
○ AE Grading per CTCAE v5.0
 
○ CRS & Neurotoxicity Grading per ASTCT Consensus Guidelines
 
○ Acute GVHD Grading per MAGIC criteria
 
○ Chronic GVHD Grading per NIH severity score
 
 
 

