**Immune Effector Cell-Associated Encephalopathy (ICE) Score**

Orientation: oriented to year, month, city, hospital: 1 point each, 4 points total				
Naming: ability to name 3 objects (e.g. clock, pen, button): 1 point each, 3 points total				
Follow Commands: can follow a simple command (e.g. show me 2 fingers): 1 point total				
Writing: can write standard sentence (e.g. Our national bird is the bald eagle): 1 point total				
Attention: can count backwards from 100 by 10: 1 point total				
Scoring				
10 = no impairment	7-9 = ICANS grade 1	3-6 = ICANS grade 2	0-2 = ICANS grade 3	0 = ICANS grade 4

ASTCT Consensus Grading for Cytokine Release Syndrome and Neurologic Toxicity Associated with Immune Effector Cells (*Biol Blood Marrow Transplant* 2019;25: 625).

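### Appendix E lists imaging-detected cerebral edema, and an ICE score of 0, under both neurotoxicity Grade 3 and Grade 4, with different management and no printed rule for choosing

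*Combined protocol and SAP*

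**What the plan says.** Section 2.0 makes neurotoxicity a secondary safety endpoint, assessed by "Neurotoxicity Grading per ASTCT Consensus Guidelines". Section 6.8 sends the reader to Appendix E for grading, evaluation and management, so that table is what the clinical team works from.

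In Appendix E each grade has one cell of criteria and one of actions:

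- Grade 3 criteria: rousing only to touch, then "ICE score 0-2 Seizure: transient Cerebral Edema on imaging".
- Grade 4 criteria: "Decreased LOC, unarousable ICE score 0 Seizure: prolonged (>5 minutes) or recurrent Cerebral Edema on imaging", followed by focal neurological deficits.
- ICE key below the table: "0-2 = ICANS grade 3" and "0 = ICANS grade 4".
- Grade 3 actions: stop the infusion, manage as Grade 2, give tocilizumab and steroids if there is concurrent CRS, and "Consider ICU care".
- Grade 4 actions: everything under Grade 3, plus consideration of high-dose steroids, treatment of the edema, and transfer to intensive care.

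Neither the table nor the key says what to do when a patient's findings point to two columns.

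**The concern.** A grading table should send a given finding to one grade. Here one imaging finding and one score value each stand in two adjacent columns, and those columns carry different instructions. Two investigators could see the same patient, record different grades and follow different actions, each in keeping with the text.

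One mismatch lies within the table itself. Edema is a Grade 3 criterion, yet the instruction to treat it appears only under Grade 4. In the Grade 3 column, and in the Grade 2 column it builds on, steroids are tied to concurrent CRS. A patient graded 3 for edema without CRS therefore meets no edema instruction and no steroid instruction in the text for that grade.

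At stake are consistent management on the ward and a reproducible Grade 3/4 split in the reported neurotoxicity results.

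**Working it through.** The plan gives no figure for this point, so there is none to reproduce. The check sets the printed entries side by side, tests whether any one reading makes them consistent, and then sizes the effect on a reported rate.

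**1. ICE scores mapped to the printed bands (Appendix E table and ICE key)**

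| ICE score | Grade(s) |
|---|---|
| 10 | none |
| 7 to 9 | 1 |
| 3 to 6 | 2 |
| 1 to 2 | 3 |
| 0 | 3 and 4 |

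Zero is the only score with two grades.

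**2. Grade 3 and Grade 4 criteria, item by item**

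| Item | Grade 3 | Grade 4 | Separated? |
|---|---|---|---|
| Consciousness | rouses only to touch | unarousable | yes |
| Seizure | transient | over 5 minutes, or recurrent | yes |
| Focal deficit | not listed | listed | yes |
| ICE score | 0 to 2 | 0 | not at 0 |
| Edema on imaging | listed, no qualifier | listed, same words | no |

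**3. Does any one reading of the table resolve this?**

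- *All items in a cell are required.* Grade 4 would then need coma, seizure, edema and focal deficit together. This is not a workable reading.
- *Any one item suffices and the higher grade wins.* Edema and ICE 0 would then always be Grade 4, and their Grade 3 entries could never operate. The rule is not printed.
- *Consciousness decides.* This places most ICE 0 patients. It does not place a patient with edema who wakes to voice or spontaneously, because those states belong to Grades 2 and 1. Nor does it place an ICE 0 patient who wakes to voice: consciousness says Grade 2 and the score says 3 or 4. The ICE key carries no consciousness condition.

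**4. Who remains ambiguous**

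The affected patients have edema on imaging or ICE 0, and none of the three features listed only under Grade 4. Within the ICE 0 group, the consciousness line narrows this further.

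**5. Size**

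Let k be the number of patients whose grade rests only on an ambiguous finding. The Grade 4 count can then differ by anything from 0 to k, and each patient moves the rate by 1/n. With n = 25 (the evaluable target in section 11.3), 1/25 = 4 percentage points. Section 11.7 reports adverse event rates with 90% intervals. For illustration, assuming no other Grade 4 cases and all k graded 4, the exact (Clopper-Pearson) 90% intervals at n = 25 are:

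| k | Grade 4 rate | 90% CI |
|---|---|---|
| 0 | 0% | 0 to 11.3% |
| 1 | 4% | 0.2 to 17.6% |
| 2 | 8% | 1.4 to 23.1% |
| 3 | 12% | 3.4 to 28.2% |

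These values of k are assumptions. The denominator is not fixed at 25 either. The safety population is everyone dosed (section 11.8) and unevaluable patients are replaced, so n may exceed 25 and the step would be smaller. If accrual ended at the 15 first-stage patients (section 11.4), the step would be 1/15 = 6.7 points.

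**6. Stopping rule**

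Section 11.5.1 counts non-hematologic events of Grade 3 or higher that are at least possibly attributable to treatment. None of its listed exceptions concerns neurotoxicity. Moving a patient between Grades 3 and 4 leaves the count unchanged.

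**The case against.** The strongest reply is that the ICE overlap is largely deliberate. Every ICE item is a task, so an unarousable patient can only score 0, and the consciousness line in the same cell tells the two grades apart. This stands for most ICE 0 patients. It does not reach those in whom consciousness and score point to different columns, and it does nothing for edema.

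Second, the management gap is narrow. Grade 4 adds to Grade 3, both stop the infusion and share the work-up, high-dose steroids are only to be considered, and the Grade 3 wording already permits intensive care. Section 6.8 asks for full evaluation of any suspected event. This is fair. What remains is considered versus directed transfer, the edema instruction and the steroid prompt.

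Third, the endpoint is defined by the cited consensus, so Appendix E is not its only definition. That is correct, and whether the consensus separates the two findings cannot be checked from the documents. Appendix E is nonetheless the table that section 6.8 tells staff to use.

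A reader might go further and infer that the Grade 4 rate of a safety endpoint is undefined, or that every patient with ICE 0 or edema is affected. The documents do not support either. No Grade 4 neurotoxicity rate is a named endpoint. Patients who are unarousable, have a prolonged or recurrent seizure or have a focal deficit meet a criterion found only under Grade 4, so the rate is bounded and open only by the ambiguous cases.

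**Conclusion.** The point holds as an internal contradiction in a grading and management table. Edema on imaging has no printed discriminator between Grades 3 and 4, and its treatment instruction sits with only one of them. ICE 0 has the same defect in the smaller group whom consciousness does not place. For patients with none of the features listed only under Grade 4, the recorded grade and the management column depend on the grader.

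The number of such patients cannot be stated, because the documents give no incidence. The figure of 4 points per patient assumes 25 dosed. The safety stopping rule, the primary CR/CRi endpoint and the futility decision are not affected, and the analyses are descriptive. It should be corrected all the same, because it bears on management and on consistent grading of a named secondary safety endpoint.

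**What to change.** Reconcile the Grade 3 and Grade 4 columns of Appendix E and the ICE key with each other and with the consensus grading that section 2.0 names. Either each finding maps to one grade, or a printed discriminator or precedence rule separates the grades. Then check that each management instruction stands in the column where its trigger is listed, the edema instruction in particular. Which grade or action applies is for the investigators to decide.

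Any neurotoxicity event already graded on edema or ICE 0 should be identified and checked against the reconciled table before the safety results are reported.

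The cost is wording in one appendix and, if such events exist, a short review of their records. No new procedure, visit or patient is needed.
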